5.3.3 Product Complaints and Medication Errors

A product complaint is a verbal, written, or electronic expression that implies dissatisfaction regarding the identity, strength, purity, quality, or stability of a drug product. Individuals who identify or suspect a potential product complaint should immediately contact Ixcelsius or designee and report the event. Whenever possible, the associated product should be maintained in accordance with the label instructions pending further guidance from an Ixcelsius or a designated quality representative.

The Investigator or his/her designee is responsible for handling the product complaint process in accordance with the instructions provided for this study in the Study Training Manual.

Product complaints and medication errors in and of themselves are not AEs. If a product complaint or medication error results in an SAE, an SAE form should be completed and sent to Ixcelsius or designee.

5.4 Blinding

5.4.1 Breaking the Blind

All study medication will be administered in a double-blind manner. Only in the case of an emergency, when knowledge of the investigational product is essential for the clinical management or welfare of the patient, the Investigator may unblind a patient's treatment assignment. If the blind is broken for any reason, the Investigator must notify the Sponsor or designee immediately after the unblinding incident without revealing the patient's study treatment assignment. In addition, the Investigator will record the date and reason for revealing the blinded treatment assignment for that patient in the electronic case report form (eCRF).

5.5 Treatment Compliance

There is no requirement for the patient to take medication every day. However, he should only take a maximum of one dose (3 caplets) per day and record this in the LogPad. The Investigator should record the amounts of study drug dispensed and returned at each visit during the treatment period. The patient should always take the 3 caplets from the same blister card with each dose. He should never take more or less than these 3 caplets per dose.

5.6 Prior and Concomitant Therapy

Use of SSRIs must be stopped, and patients who were previously taking SSRIs regularly require an additional 4-week washout prior to the 4-week run-in period. Patients who require SSRI treatment for depression or other illnesses (not PE) should not be included in the study.

Concomitant treatment with PDE5 inhibitor (eg, sildenafil, tadalafil, vardenafil), topical anesthetics, and/or tramadol is prohibited. Additionally, any history (current or last 6 months) of use of Botox or similar product to treat PE is not allowed.

The following treatments are also prohibited during the study: monoamine oxidase inhibitors, alpha blockers, 5-alpha reductase inhibitors (including finasteride [Propecia] for hair loss). Herbal supplements are also prohibited.

Concomitant use of potent or moderate CYP3A4 inhibitors (eg, ketoconazole, itraconazole, ritonavir) and inducers (eg, bosentan, carbamazepine, phenytoin, phenobarbital, St John's Wort, and rifampicin) is not allowed from at least 4 weeks before the start of dosing until the end of the study.

6 Study Assessments and Procedures

6.1 Study Visits

A complete listing of study measurements and evaluations may be found in the Schedule of Events (Table 13-1).

Screening Visit 1

Approximately 28 days (± 3 days) prior to the first dosing, patients will attend the center for assessment of eligibility for the study. Written informed consent must be obtained from each potentially eligible patient by study site personnel prior to the initiation of screening procedures as outlined in this protocol.

Note: Patients taking chronic SSRIs for the treatment of PE must have an additional 4-week washout prior to the 4-week run-in period.

After providing signed written informed consent, patients will complete screening assessments. Each patient who undergoes screening for study enrollment will be assigned an identification number, which will provide a means of identifying each patient. Information and data collected will include the following:

- Assessment of patient eligibility according to the entry criteria, including clinical interview by the Investigator or his/her qualified designee to indicate that the patient meets the ISSM definition of PE. In particular, the investigator should ask the patient about the duration of the symptoms of PE, since lifelong PE can only be diagnosed if ejaculation always or nearly always occurred prior to or within about 1 minute of vaginal penetration from the earliest sexual experience.
- Medical history and assessment of concomitant medication.
- Year and month of birth, gender at birth, and race (ethnicity).
- Height, weight and physical examination. A physical examination will be conducted by the Investigator or other licensed study site personnel to establish an overall profile of the

patient's health and to identify and document any abnormal physical findings prior to the patient's participation in the study.

- Recording of vital sign data (heart rate and blood pressure measurements).
- 12-lead ECG.
- Blood sampling for laboratory safety tests (including hematology and clinical chemistry analyses) and serology for HBsAg, HCV Ab, HIV 1, and HIV 2.
- Urinalysis.
- Urine drug screen.

Patients willing to take part in the study and who are eligible according to the criteria already assessed during the screening visit will be provided with a LogPad and stopwatch. They will complete training on how to use the LogPad during this visit. Once the training is completed, patients will be asked to attempt intercourse with their partners at least 4 times during the 4-week run-in period, to use the stopwatch to time the attempt, and to record the relevant details in the LogPad including whether alcoholic drinks were taken prior to intercourse. At the next study visit (Visit 2), the patient must bring the LogPad to the study site. Further details for LogPad use and instructions are found in the Study Training Manual.

Baseline Visit 2

On Visit 2 (Day 0, Week 0 \pm 7 days from screening), patients will attend the study center, and information and data collected will include the following:

- Assessment of patient eligibility according to the IELT entry criteria. The patient will return the LogPad to the investigator. The LogPad will provide a summary of the IELT data collected during the run-in period and will indicate whether the patient is eligible to continue in the study based on the IELT criteria. (Note: Refer to the Study Training Manual for instructions if a patient does not remember to return the LogPad.)
- The investigator will provide the LogPad back to the patient for completion of the PEP, PGIS, IIEF, and PHQ-9. After completion of these questionnaires, the patient will return

the LogPad to the investigator. The LogPad will provide a further summary that will indicate whether the patient is eligible to continue in the study based on the results of the PEP, IIEF, and PHQ-9. If the patient is not eligible based on these assessments, then he should not be randomized or continued in the study, and the investigator may discuss alternate treatment options.

- Weight.
- Physical examination.
- Recording of vital sign data (heart rate, blood pressure, and oral temperature measurements) and 12-lead ECG.
- Blood sampling for laboratory safety tests (including hematology, clinical chemistry, and coagulation analyses).
- Urinalysis.
- Urine drug screen.
- C-SSRS.
- Adverse events and concomitant medication update.
- The patients who meet all of the eligibility criteria will be randomized and assigned a treatment number. Eligible patients will be provided with at least 7 doses of study drug (IX-01 or placebo). Further supplies can be dispensed at this visit based on a discussion between the Investigator and patient but the maximum allowed dose is 1 dose (3 caplets) per day. Each dose of study drug comprises 3 caplets contained within a discrete blister card. Patients must be informed that 1 dose is all 3 caplets, and the dose should be taken with water at least one hour before or after food. Patients should attempt sexual intercourse approximately 1 to 6 hours after taking the dose. The patients will also be provided with a LogPad. Patients should be reminded on the instructions for using the stopwatch and also the LogPad to record their usage of the study medication, as well as all occasions that they attempt sexual intercourse and whether alcoholic drinks were

taken. Patients will be asked if they are willing to try intercourse with their partner approximately 8 times or more between Visit 2 and Visit 5 although less than 8 attempts will not be classified as a protocol deviation. Patients should be reminded to bring their LogPad and any unused study medication back to the study site for Visit 3.

Visit 3

- Patients will return to the study center on Day 14 \pm 3 days (Week 2). The patients will be asked for information on any AEs that have occurred or are occurring and concomitant medication usage since Visit 2. The remaining study medication will be collected, and a check of the quantity remaining will be performed. After completion of all assessments, the patient will receive enough medication to take at least 7 doses of study drug (IX-01 or placebo). Further supplies can be dispensed at this visit based on a discussion between the Investigator and patient but the maximum allowed dose is 1 dose (3 caplets) per day. (Note: Refer to the Study Training Manual for instructions if a patient does not remember to return the LogPad.)
- The patient will return the LogPad.
- The investigator will provide the LogPad back to the patient for completion of the PHQ-9. Once complete, the patient will return the LogPad to the investigator.
- If the results of the PHQ-9 indicate a change in mental condition and/or if the investigator suspects a deleterious change in mood (see Section 13.2), the investigator must administer the C-SSRS.
- Physical examination. Any changes in physical findings that meet the definition for an AE and that occur after the patient initiates investigational product will be recorded as AEs in the eCRF.
- Blood sampling for laboratory safety tests (including hematology and clinical chemistry analyses).
- Adverse events and concomitant medication update.

Visit 4

- Patients will return to the study center on Day 28 \pm 7 days (Week 4). The patients will be asked for information on any AEs that have occurred or are occurring and concomitant medication usage since Visit 3. The remaining study medication will be collected, and a check of the quantity remaining will be performed. After completion of all assessments, the patient will receive enough medication to take at least another 14 doses of study drug (IX-01 or placebo). Further supplies can be dispensed at this visit based on a discussion between the Investigator and patient but the maximum allowed dose is 1 dose (3 caplets) per day. (Note: Refer to the Study Training Manual for instructions if a patient does not remember to return the LogPad.)
- The patient will return the LogPad.
- The investigator will provide the LogPad back to the patient for completion of the PEP, PGIS, IIEF, and PHQ-9. Once complete, the patient will return the LogPad to the investigator.
- If the results of the PHQ-9 indicate a change in mental condition (or the investigator suspects an adverse change), the investigator should administer the C-SSRS and determine if the patient may remain in the study.
- Physical examination.
- Recording of vital signs data (heart rate and blood pressure measurements).
- Blood sampling for laboratory safety tests (including hematology and clinical chemistry analyses).
- Urinalysis.
- Adverse events and concomitant medication update.

Visit 5 (End of Treatment or Early Termination)

Note that if a patient is discontinued from the study at any time during the treatment period earlier than expected, then he must return to the study site and complete an early termination visit (Visit 5).

- Patients will return to the study center on Day 56 ± 7 days (Week 8). The patients will be asked for information on any AEs that occurred or are occurring and concomitant medication usage since Visit 4. The patient must return the LogPad. The remaining study medication will be collected. The LogPad will be checked and retained at the study center. (Note: Refer to the Study Training Manual for instructions if a patient does not remember to return the LogPad.)
- The investigator will provide the LogPad back to the patient for completion of the PEP, IIEF, PHQ-9, PGIS and CGIC. After completion, the patient will return the LogPad to the investigator.
- If the results of the PHQ-9 indicate a change in mental condition (or the investigator suspects an adverse change), the investigator should administer the C-SSRS.
- Weight.
- Physical examination.
- Recording of vital sign data (heart rate and blood pressure measurements) and 12-lead ECG.
- Blood sampling for laboratory safety tests (including hematology and clinical chemistry analyses).
- Urinalysis.
- Urine drug screen.
- Adverse events and concomitant medication update.

End of Study Visit 6 (Follow Up)

Patients will return to the study center for a follow-up visit on Day 70 \pm 7 days (Week 10), and the following assessments will be performed approximately 2 weeks after the last visit:

- Weight.
- Physical examination.
- Recording of vital sign data (heart rate and blood pressure measurements) and 12-lead ECG.
- Blood sampling for laboratory safety tests (including hematology and clinical chemistry analyses).
- Urinalysis.
- Adverse events and concomitant medication update.
- C-SSRS, only if clinically indicated per the protocol.

6.2 Efficacy Assessments

Outcome measures included during treatment include results from the use of the following:

- Stopwatch to measure IELT.
- LogPad (e-diary) to record summary of study drug intake and details of sexual intercourse attempts (including IELT and two PEP questions (control and ejaculation-related personal distress)).
- Responses to the PEP questionnaire.
- Responses to PGIS questionnaire.
- Responses to the CGIC questionnaire.

IELT

The IELT is the time from the start of intercourse (penetration) until ejaculation and is recorded by the patient or partner using the stopwatch provided. At the start of the run-in phase, the patient and partner should decide who will activate the stopwatch and subsequently stop the stopwatch to record the timing of intercourse. The same person should start and stop the stopwatch with every intercourse attempt throughout the study until Visit 5.

LogPad

The LogPad has been specifically designed to enable patients to record details of sexual intercourse attempts and study drug use throughout the study. The key data to be recorded by the patients are date and time of study drug caplets taken, date and time of any intercourse attempt, IELT, level of control of timing of ejaculation; and level of ejaculation-related personal distress. The patient also will use the LogPad at each study visit to complete the PEP, PGIS, IIEF, and PHQ-9 (PEP, PGIS and IIEF are not completed at Visit 3/Week 2). At the final treatment visit (Visit 5 or Early Termination), the CGIC is also collected via the LogPad. For further details of the LogPad design and function, refer to the Study Training Manual.

PEP

The PEP is a widely used self-administered tool that includes measures of perceived control over ejaculation, ejaculation-related personal distress, ejaculation-related interpersonal difficulty, and satisfaction with intercourse. It has been used in many previous studies of PE and is considered validated for this purpose. All of the domains are relevant to a patient with PE, and the instrument has the advantage of being simple and quick to use.¹⁴ In this study an additional exploratory question on bother will be included in the 4-week recall version used at baseline, week 4 and week 8.

PGIS

The Patient Global Impression of Severity is a questionnaire that asks the patient to assess the severity of their condition (categories of response are no PE, mild, moderate, severe).

CGIC

The Clinical Global Impression of Change (CGIC) (also referred to as PGIC) is a simple and validated instrument that allows the patient to rate the change in his condition (PE) at the end of treatment on a 7-point scale ranging from “much worse” to “much better.”¹⁵ In this study the CGIC will be administered after the PEP at the final visit and will include two additional questions. See Appendix 2.

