Until recently, there has been no universally accepted definition of PE. Generally, definitions of PE acknowledge certain core components: short ejaculatory latency, lack of control over ejaculation, and ejaculation-related personal bother or distress. The Diagnostic and Statistical Manual of Mental Disorders, Fifth Edition (DSM-5), published in 2013, defines the condition as persistent or recurrent pattern of ejaculation occurring during partnered sexual activity within approximately one minute following vaginal penetration and before the individual wishes it, and is associated with clinically significant distress in the individual. The International Consultation on Sexual Dysfunctions suggests that men with an intravaginal ejaculatory latency time (IELT) less than 2 minutes qualify as having PE.³ Over the last few years, there has been a new evidence-based definition that has gained widespread acceptance. It is the definition adopted by the International Society for Sexual Medicine (ISSM), and defines PE as a male sexual dysfunction characterized by ejaculation which always or nearly always occurs prior to or within about one minute of vaginal penetration (lifelong PE) OR a clinically significant reduction in latency time, often to about 3 minutes or less (acquired PE), and the inability to delay ejaculation on all or nearly all vaginal penetrations, and negative personal consequences, such as distress, bother, frustration, and/or the avoidance of sexual intimacy.⁴ The definition applies to both lifelong and acquired PE but is limited to intravaginal sexual activity. The ISSM definition is similar to the DSM-5.

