4.1 Selection of Study Population

4.1.1 Inclusion Criteria

Each patient must meet all of the following criteria to be enrolled in this study:

1. Men aged ≥ 18 years and ≤ 60 years in stable (≥ 6 months) heterosexual relationship and who have lifelong PE.
2. Premature ejaculation confirmed by IELT ≤ 1 minute on $\geq 75\%$ attempts at sexual intercourse during the run-in period.
3. Patient meets other aspects of ISSM definition including inability to delay ejaculation on all or nearly all vaginal penetrations and negative personal consequences such as distress, bother, and frustration.
4. Patient and partner willing to attempt intercourse at least 4 times during the run-in period and at least 8 additional times during the double-blind part of the study.
5. Partner not planning pregnancy and willing to use contraception (unless not of childbearing potential, eg, surgically sterilized).
6. Patient willing to limit use of alcohol on days in which he takes study drug (not more than 3 standard drinks as defined in the Informed Consent Form).
7. Patient capable of giving written informed consent.

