4.1.2 Exclusion Criteria

1. Any IELT value > 2 minutes during the run-in period.
2. Any patient making < 4 attempts at sexual intercourse during the run-in period (screening may be extended or patient may be rescreened if there are extenuating circumstances).
3. Any patient who rates his control of ejaculation as fair, good, or very good (PEP question administered at the end of the run-in period).
4. Any patient who rates his ejaculation-related “personal distress” as “not at all” or “a little bit” (PEP question administered at the end of run-in period).

5. Coexisting Erectile Dysfunction (IIEF Erectile Function domain <22 during the run-in period).
6. Concomitant use of phosphodiesterase type 5 (PDE5) inhibitors, SSRIs/selective serotonin norepinephrine reuptake inhibitor (SSNRIs), monoamine oxidase inhibitors, alpha blockers, 5-alpha reductase inhibitors, topical anesthetics, and/or tramadol.
7. Any history (last 6 months) of use of Botox or similar product to treat PE.
8. Any patient who has received IX-01 in a previous clinical study.
9. Any patient who is unwilling to stop other treatments for PE (including but not limited to pharmacological, sex therapy, psychotherapy multiple condoms, and prior masturbation).
10. Any other sexual disorder of patient or partner that could interfere with results.
11. Any current sexually transmitted disease.
12. Any major medical condition of patient that could interfere with ability to have sexual activity and/or require hospital treatment.
13. Body mass index (BMI) >40 kg/m² or weight <60 kg.
14. Participation in a clinical drug study anytime during the 30 days prior to screening.
15. History of or positive test results for Human immunodeficiency virus (HIV), hepatitis B.
16. History of prostate disease or clinically significant prostate disease.
17. History of myocardial infarction, coronary bypass surgery, coronary artery angioplasty, unstable angina, clinically evident congestive heart failure, cardiac pacemaker, or cerebrovascular accident.
18. Cardiac arrhythmia: significant cardiac arrhythmia shown on screening ECG, or a known or suspected history of significant cardiac arrhythmias.
19. History of drug-induced allergic reactions including skin reactions.
20. History of congenital QT prolongation and/or corrected QT interval >450 msec at screening visit using the Bazett formula.

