7.2.2 Other Secondary Efficacy Endpoints

The following other secondary efficacy endpoints will be analyzed:

1. Fold change from baseline in (arithmetic) mean IELT over the treatment assessment period.
2. Change from baseline in (arithmetic) mean IELT over the treatment assessment period.
3. Proportion of patients with GM IELT of ≥ 1 minute over the treatment assessment period.
4. Proportion of patients with GM IELT of ≥ 2 minutes over the treatment assessment period.
5. Proportion of patients with GM IELT of ≥ 3 minutes over the treatment assessment period.
6. Proportion of patients with GM IELT of ≥ 4 minutes over the treatment assessment period.
7. Proportion of patients with GM IELT of ≥ 5 minutes over the treatment assessment period.
8. Proportion of patients with GM IELT increase over the treatment assessment period of ≥ 45 seconds compared with baseline.
9. Proportion of patients with GM IELT increase over the treatment assessment period of ≥ 1 minute compared with baseline.
10. Percentage of intercourse attempts lasting > 1 minute over the treatment assessment period.
11. Percentage of intercourse attempts lasting > 2 minutes over the treatment assessment period.
12. Percentage of intercourse attempts lasting > 3 minutes over the treatment assessment period.
13. Percentage of intercourse attempts lasting > 4 minutes over the treatment assessment period.
14. Percentage of intercourse attempts lasting > 5 minutes over the treatment assessment period.
15. Proportion of patients improving on PGIS
16. Proportion of patients achieving ≥ 1 category of improvement from baseline to end of treatment in each of the following (from 4-weekly PEP questionnaire):

- a. Satisfaction with sexual intercourse
 - b. Control over ejaculation during sexual intercourse
 - c. Ejaculation-related distress
 - d. Ejaculation-related interpersonal difficulty
 - e. Ejaculation-related bother
17. Change in score from baseline in each of the following (from 4-weekly PEP questionnaire):
- a. Satisfaction with sexual intercourse
 - b. Control over ejaculation during sexual intercourse
 - c. Ejaculation-related distress
 - d. Ejaculation-related interpersonal difficulty
 - e. Ejaculation-related bother

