13.2.3 International Index of Erectile Function (IIEF)

These questions ask about the effect your erection problems have had on your sex life **over the past 4 weeks**. Please answer these questions as honestly and as clearly as possible. Please answer every question by checking the appropriate box. If you are unsure about how to answer, please give the best answer you can.

In answering these questions, the following definitions apply:

* **Sexual intercourse**

Is defined as sexual penetration of the partner.

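### Do the run-in eligibility rules break down for an attempt that ends in ejaculation before penetration?

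*Combined protocol and SAP*

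**What the plan says.** - Section 6.2 (IELT): "The IELT is the time from the start of intercourse (penetration) until ejaculation". No value is assigned to an attempt that does not reach penetration.
- Section 4.1.1, inclusion 2, requires an IELT of 1 minute or less on at least 75% of run-in attempts. Section 4.1.2, exclusion 2, removes men with fewer than 4 "attempts at sexual intercourse during the run-in period (screening may be extended or patient may be rescreened if there are extenuating circumstances"). Both rules count attempts.
- Section 1.1 gives the ISSM definition of lifelong PE as "ejaculation which always or nearly always occurs prior to or within about one minute of vaginal penetration". Section 6.1 (Screening Visit 1) makes this the investigator's test: "ejaculation always or nearly always occurred prior to or within about 1 minute of vaginal penetration from the earliest sexual experience".
- Section 6.1 (Baseline Visit 2): the LogPad summarizes the run-in IELT data and "will indicate whether the patient is eligible to continue in the study based on the IELT criteria". The algorithm is not printed. Sections 6.1 and 6.2 send LogPad instructions, design and function to the Study Training Manual.
- Section 13.2.3 (IIEF) says of sexual intercourse: "Is defined as sexual penetration of the partner". That definition is offered for answering that questionnaire.
- Section 7.4 requires two analyzable postbaseline IELTs for the mITT set, with blinded allocation before database lock. Section 7.2.2, items 10 to 14, uses "Percentage of intercourse attempts lasting" longer than a threshold.

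**The concern.** The definition of the disease covers ejaculation before penetration, while the measurement that confirms the disease starts at penetration. A man whose run-in includes such an attempt is among those the trial means to recruit, yet the attempt yields no number to compare with 1 minute. If the LogPad treats a blank as a failure, or does not count it as an attempt, men at the severe end could be turned away and more would have to enter the run-in to reach 220. If instead a zero were stored, the geometric mean for that period would be zero, and a fold change from a zero baseline would be undefined. The mITT count and the denominator of the percentage endpoints raise the same question.

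**Working it through.** **The plan's own figure.** The only related figure is the power statement in Section 7.3 (45 s, SD 70 s, two-sided 0.05). For 44 v 44 the standard error is 70 × √(1/44 + 1/44) = 14.92 and Φ(45/14.92 − 1.96) = 85.4%. For 44 v 66 it is 13.62, giving 91.0%. Both agree with the stated 85% and 90%, and neither depends on this point.

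**Four readings of an attempt that ends before penetration**
- *Strict*: an attempt, but without a qualifying IELT.
- *Penetration-only*: not an attempt.
- *Definitional*: an attempt that meets the 1-minute criterion.
- *Timed-only*: counts toward the 4, left out of the 75%.

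| Attempts ≤60 s / 61–120 s / before penetration | Strict | Penetration-only | Definitional | Timed-only |
|---|---|---|---|---|
| 3 / 0 / 1 | pass, 3/4 | fail, 3 attempts | pass, 4/4 | pass, 3/3 |
| 2 / 0 / 2 | fail, 2/4 | fail, 2 attempts | pass, 4/4 | pass, 2/2 |
| 3 / 1 / 1 | fail, 3/5 | pass, 3/4 | pass, 4/5 | pass, 3/4 |
| 2 / 1 / 1 | fail, 2/4 | fail, 3 attempts | pass, 3/4 | fail, 2/3 |

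So the verdict does depend on the reading.

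**How well each reading is supported.** Penetration-only rests on the IIEF definition, which is confined to that questionnaire. IIEF question 3 asks how often penetration was achieved when intercourse was attempted, so even there an attempt need not reach penetration. The other three are nested. A record that passes strictly also passes timed-only, and one that passes timed-only also passes definitionally (a man with no timed attempt at all has no timed-only percentage).

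**Size.** The frequency q is not in the documents; 2%, 5% and 10% are assumed. Let k of n attempts end before penetration, all others at or below 60 s. Strict fails if (n − k)/n < 0.75; penetration-only fails if n − k < 4; definitional never fails. k is binomial, or beta-binomial with parameters q and 1 − q (correlation 0.5).

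- n = 4, q = 5%, independent: strict 1 − 0.95⁴ − 4 × 0.05 × 0.95³ = 1.4%; penetration-only 1 − 0.95⁴ = 18.5%.
- n = 4, q = 5%, correlated: strict 5.5%, penetration-only 10.1%.
- n = 4, strict, over q = 2% to 10%: 0.2% to 5.2% independent, 2.2% to 11.2% correlated.
- Otherwise eligible men needed (n = 4, q = 5%, correlated): strict 220/(1 − 0.055) = 233; penetration-only 220/(1 − 0.101) = 245; definitional 220.

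Four attempts is the permitted minimum. In the proof-of-concept study (Section 1.3.5) men took a mean of 13.0 to 14.6 doses in 8 weeks, about 6.5 to 7.3 per 4 weeks; this is a rough proxy, since these are doses on treatment with a wide range. At n = 7 and q = 5%, penetration-only falls to 0.02% (independent) or 4.0% (correlated). Strict does not shrink: 4.4% and 7.9%.

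If 10% of timed attempts last 60–120 s (assumed), then at n = 4 and q = 5% the strict, penetration-only and definitional readings disagree for 18.1% of men (independent) or about 10% (correlated). Without penetration-only this drops to 5.6% and 6.6%.

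**Primary comparison.** A simulation used 44 v 66 men, 5 attempts per period and at least 2 timed attempts in each. Assumed inputs: log baseline N(ln 28, 0.45); within-man log SD 0.35; log fold N(ln 2.3, 0.80) on drug and N(ln 1.35, 0.60) on placebo. The model had treatment and baseline GM, no site effect; 4000 trials per cell. With these attempts left out of the GM and q = 2% to 10%, the effect is 48.0 to 48.4 s and power 90% to 93%, against 48.6 s and 93% with none. Entering zeros would matter (38.2 s and 79% at q = 10%, correlated), but nothing in the plan directs this and the IELT definition gives such an attempt no value.

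**The case for a change.** Eligibility criteria should be readable from the protocol, and an analysis plan cannot repair a decision made before randomization. The option to extend or rescreen is attached to the 4-attempt rule and not to the 75% rule. A literal check of a blank IELT against 1 minute gives the strict reading, whose failure share does not fall as attempts increase. If the LogPad does not separate these attempts from missing times, they may not be recoverable later. Writing the rule down would cost little.

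Most of this stands as description: the text is silent, and strict and definitional counting differ. It does not show a stated rule that gives a wrong result. The Study Training Manual, to which the protocol sends LogPad function, was not available for this review, so absence of a rule is not established. Sections 1.1 and 6.1 already point to the definitional count. A shortfall in attempts may be cured by extension, so the 245 above treats possibly recoverable men as lost.

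A heavier remedy would also cost something. Requiring 2 timed run-in IELTs for a baseline GM, combined with definitional counting, would remove after randomization men who have one timed attempt and hence a computable baseline under the present text. At 4 attempts and q = 5%, 0.05% (independent) or 3.1% (correlated) of men have fewer than 2 timed attempts.

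**Conclusion.** No change to the plan follows. This is a missing operational detail that those who build the LogPad check and the analysts can fill sensibly from Sections 1.1, 6.1 and 6.2. The run-in rules act before allocation and alike on all arms, so no between-arm bias arises, and the target of 220 stands. For the primary endpoint, leaving out an attempt that has no IELT by definition is adequate. What counts as analyzable in Section 7.4 is settled blinded before database lock, and the denominator in items 10 to 14 affects other secondary endpoints only.

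The number of men affected cannot be estimated from the documents. The shares above rest on an assumed frequency of 2% to 10%, an assumed correlation of 0 or 0.5 and, for the headline cases, exactly 4 attempts. The simulation has no run-in eligibility step and no link between these attempts and IELT. It supports the adequacy of the literal reading for the comparison between arms and says nothing about who is recruited.
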